7.5.1 Ambulatory blood pressure monitoring	
7.5.2 Home-based monitoring	
7.5.3 Clinic-based monitoring	
7.6. Patient follow up and study period	22
8. Schedule of assessment (refer annexure)	22
9. Study endpoints and outcomes	22
10. Criteria for withdrawal from the study	26
11. Safety assessment	26
12. Statistical considerations	26
Sample size calculation	
Statistical analysis plan	
13. Ethical considerations	27

14. Reporting of adverse events	28
15. Regulatory considerations	28
16. Operational considerations 16.1 Data management 16.2 Protocol deviation and violation 16.3 Publication policy	29
17. References	30
18. List of annexures a) Schedule of assessments and visits b) SF-36 questionnaire c) Perceived stress scale questionnaire d) Montreal Cognitive assessment e) List of green foods f) List of supplements	31

Lists of tables and figures

Figure-1	Study design	8
Table-1	Grades of hypertension	13
Table-2	Classification of hypertension risk based on risk factors, end organ damage.	13
Table-3	Stepwise approach for adding antihypertensive medications (standard care)	14
Table-4	Antihypertensive medicines escalation and de-escalation protocol (Intervention arm)	17
Table-5	Doses of commonly used antihypertensive medications	21

Design synopsis

Study design
 
Multicentre, open label, randomised controlled trial
	
Sample size
 
104 in standard care 208 in the intervention arm
 
Allocation ratio 1:2

Number of centres
 
Approximately 5 to 10 sites
 
Duration of Program
 
Run in period- 2 to 3 weeks
 
Duration of intervention- 2 years
 
Duration of follow up- one year
	
Number of groups: 2
 
Group 1 Standard care arm
 
Lifestyle modifications and medications as per current guidelines
 
Group 2 Intervention arm
 
Twin Precision treatment along with the standard of care


Details of intervention (Twin Precision treatment)
 
The platform collects data from body sensors and a mobile app to track and analyze the body's health signals to personalize patients' treatment.
 
Individualized medicine, exercise, sleep and nutritional syntax of the Twin Precision Treatment program guided by artificial intelligence will be
	
Details of standard care (as per ISH 2020 guidelines)
 
Lifestyle modifications will focus on
 
 ● Weight loss for optimal BMI, ● Physical activity of 150 min/week ● Salt reduction ● Avoid smoking, alcohol 
Pharmacological therapy:
 
A= ACE inhibitor or ARB
 
B = Beta blocker

administered.	
C = Calcium channel blocker
 
D = Diuretics

Study population:
 
 ● Patients with hypertension ● Monotherapy or more than one drug as well not on medications ● Well-controlled or controlled 	
Key exclusion criteria
 
 ● Uncontrolled hypertension (> 180/110 mm of Hg) ● H/o hypertensive emergency requiring admission / Resistant Hypertension ● Diabetes mellitus ● Heart failure with EF < 40%

Primary outcome
 
Change in blood pressure* 1-year post-randomisation
 
* Both ABPM 24 hour and at clinic BP
	
Secondary outcomes
 
 ● Change in blood pressure* 6 months and two years post-randomisation ● Requirement of antihypertensive medications ● Change in metabolic parameters ● Inflammatory markers ● Hypertension mediated organ damage (Brain, cardiac, kidney and eye) assessment ● Major adverse Cardiac outcomes

Protocol signature page

Study title: Efficacy and safety of Twin Precision treatment in patients with hypertension- a multicentric, open-label, randomised controlled trial

I have read this protocol and agree that it contains all necessary details for carrying out the study as described. I will conduct the study as outlined therein, including all statements regarding confidentiality. I will make a reasonable effort to complete the study within the time designated. I will provide copies of this protocol and all pertinent information to the study personnel under my supervision. I will discuss this material with them and ensure they are fully informed regarding the device and the conduct of the study.

I will conduct the study in accordance with the protocol, the Declaration of Helsinki and applicable local requirements.

Principal Investigator :

Job title: Senior Consultant

Institution:

Address:

Signature:

Date:

2. Introduction and background

Hypertension is the leading cause of cardiovascular disease and premature deaths worldwide. (1) According to WHO, globally, 1.13 billion people have hypertension, and it was estimated in 2015 that every 1 in 4 males and 1 in 5 females had hypertension. Even worse is that fewer than 1 out of 5 patients with hypertension had control in blood pressure. (2)

Elevated blood pressure arises from a combination of genetic and environmental risk factors. (3) Some risk factors include high salt intake, low potassium intake, sedentary lifestyle, obesity, unhealthy diet and alcohol consumption. (1) Also, patients with hypertension exhibit insulin resistance and hypertriglyceridemia compared to normotensive controls. While antihypertensive medications effectively control blood pressure, they are ineffective in preventing complications and do not effectively improve insulin resistance. (4) Also, the role of insulin resistance in diabetes has shown non-diabetic hypertensive patients have significantly higher plasma insulin concentrations than normotensive subjects. (5)

Nutrition based therapy and lifestyle modifications serve as the first line of treatment for prevention as well as to control blood pressure in stage 1 hypertension. (6) Dietary modifications have been widely considered an important step in the lifestyle modification strategy for prevention of hypertension. It also has the advantage of a lesser cost requirement than pharmacological therapy and without any side effects associated with antihypertensive medications. Several dietary patterns (such as DASH diet and Mediterranean diet) and strategies in the supplementation of macro and micronutrients have been tried with varied success. (3)

DASH trial: was conducted in a subgroup of 133 patients with SBP between 140-160 mm Hg and DBP between 90-95 mm Hg. All patients were given control diet for 3 weeks followed by randomisation to receive 8 weeks of either control diet (rich in fruits and vegetables) or combination diet rich in fruits, vegetables, and low-fat dairy products, including whole grains, fish, poultry, and nuts, and reduced in fats, red meats, sweets, and sugar-containing beverages. Both the control diet and combination diet significantly reduced blood pressure with much higher effect seen with combination diet. Control diet reduced systolic BP (-7.2 mm Hg, $P < .001$) and diastolic BP (-2.8 mm Hg, $P = .013$) and combination diet reduced systolic BP (-11.4 mm Hg, $P < .001$) and diastolic BP (-5.5 mm Hg, $P < .001$). (6)

PREDIMED trial: Studied the effect of mediterranean diet in 772 participants between 55- 80 years of age. Two forms of Mediterranean diet (with extra-virgin olive oil or nuts) was compared with low fat dietary on cardiovascular disease and blood pressure. There was a significant reduction in SBP of -5.9 mm Hg (CI, -8.7 to -3.1 mm Hg) in the Mediterranean diet with olive oil group and -7.1 mmHg (CI, -10.0 to -4.1 mmHg) in the Mediterranean diet with nuts group. (7)

3. Rationale for the study

While these studies have looked at the effect of dietary intervention on reduction in blood pressure, and have not focused on the reversal of hypertension. With Digital Twin technology - powered by the Internet of Things and Artificial Intelligence - we will be studying reversal of hypertension through improvement of metabolic health.

The TPT attempts to improve blood pressure control by measuring and treating the dysfunctional metabolism in the hypertensive patient. Using Digital Twin technology powered by artificial intelligence (AI) and Internet of Things (IoT) technologies, the Whole Body Digital Twin Platform captures data on up to 174 health markers, up to 3000 daily data points to provide precision nutrition guidance to the patient that precisely balances 87 essential nutrient factors to optimize the metabolic functioning of the patient. Additionally the Whole Body Digital Twin platform also captures daily physical activity and sleep data, and provides precision guidance on activity and sleep for the patient to follow.

In an ongoing diabetic trial involving Twin nutrition, we found that the intervention was able to achieve good reduction in systolic and diastolic blood pressure along with reduction of antihypertensive medications. Hence, we intend to look at the efficacy of the program on hypertensive patients without diabetes in this trial.

4. Objectives of the study

4.1. Primary Objective

1. To compare the mean change in systolic and diastolic 24 hr blood pressure ambulatory from baseline to 1 year between the 2 groups
2. To compare the mean change in systolic and diastolic blood pressure clinic based from baseline to 1 year between the 2 groups

4.2. Secondary Objective

Blood pressure and antihypertensive medication related

1. To compare the mean change in systolic and diastolic blood pressure between the 2 groups from baseline to 6 months and 2 years post randomization
2. To compare the proportion of patients having adequate control of hypertension at end of 1 year and 2 years

3. Among those with adequate control, to compare the de-escalation of dose or reduction in the number of antihypertensive medications from baseline to 6 months, 1 year and 2 years in both the groups
4. To study the frequency of introduction of new antihypertensive medications or dose escalation of existing antihypertensive medications in both the groups

Metabolic parameters and biomarkers based

5. To study the effect of Twin Precision treatment on change on metabolic parameters
6. To study the effect of Twin Precision treatment on change in cardiac and renal biomarkers

Quality of life and Safety related

7. To study the safety of Twin Precision treatment on antihypertensive drug withdrawal
8. To compare the change in quality of life and treatment satisfaction between the 2 groups

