4.3 Exploratory objective

1. To study the change in exploratory biomarkers between the 2 groups
 - Endothelial function based biomarkers
 - Stress based biomarkers
 - Inflammatory biomarkers
 - Hormones, Vitamins and minerals
2. To study the incidence of hypertension mediated organ damage (brain, heart, kidney, artery, eyes)

5. Study design: Multi centric, open label, parallel arm randomized controlled trial

[figure not shown]

Figure-1 Study design

Study period: The total study period will be for approximately 3 years as follows:

Run in period: 2-3 weeks

Intervention period: 2 year

Passive Follow up: 1 year

After screening, all eligible patients will have a mandatory 2-3 weeks run-in period with existing therapy (standard care) for stabilization of blood pressure and for baseline continuous glucose monitoring. Patients with blood pressure >180/110 mm Hg at the end of 3 weeks run-in period will be considered as screen failure.

Number of groups:

Group A (Standard care arm): Will receive medications for hypertension along with lifestyle modifications as per existing guidelines

Group B (Intervention arm): Will receive Twin Precision Treatment along with standard care

6. Eligibility criteria

Inclusion criteria

1. Patients with diagnosis of primary hypertension (either adequately controlled or inadequately controlled with blood pressure \leq 180/110 mm Hg); both treatment naive & on treatment (includes monotherapy or multiple drugs)
2. Age 18 years and above
3. Of either gender
4. Willing to follow study specific activities and able to handle smartphone

Exclusion criteria

Patients with the following criteria will be excluded.

1. Uncontrolled hypertension ($>$ 180/110 mm of Hg) or history of hypertensive emergency requiring admission
2. Hypertension due to secondary causes
3. History of Diabetes mellitus (when either of the following criteria is met: on medications to control blood sugar or FBS $>$ 126 mg/dl; RBS $>$ 200 mg/dl; HbA1c \geq 6.5)
4. Symptomatic heart failure or EF $<$ 40%
5. Chronic kidney disease (eGFR less than 60 ml/min/1.73 m²) or history of any major renal anomalies like unilateral kidney, polycystic kidney
6. Any major cardiovascular event in the last 6 months (such as MI, stroke, TIA)
7. Hypertensive Retinopathy (grade 3 and above)
8. Weight loss more than 5% in 3 months
9. Arm circumference too large or small to allow accurate BP measurement with available devices

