Dose reduction or withdrawal of antihypertensive drugs will be considered when the patient reaches the target blood pressure. The dose reduction is in accordance with the protocol described by Nelson et al. i.e half dose reduction at weekly intervals with weekly assessment until the lowest dose is reached followed by withdrawal. The period of withdrawal will range from 2 weeks to 4 weeks.

Target blood pressure for our study will be considered as 130/80 mm Hg for young individuals and 140/90 mm Hg for elderly (65 and above) -2020 International Society for Hypertension Global Hypertension Practice Guidelines

Table-4 Antihypertensive medicines escalation and de-escalation protocol

Tier number	Medicines	Initial condition on enrolment	Reduction condition	Increase conditions
Tier 0	No medicine	Initial no medicine & BP < 160/100 mm Hg		Move to Tier 1, if (5d-BP > 135/85) & (after staying in this tier for 5 days)
Tier 1	Monotherapy (A)	Monotherapy	Move to Tier 0, if ((1d-BP < 135/85 for 7 consecutive days) II (1d-BP < 90/60 for 3 consecutive days) II (Symptoms of Hypotension like Postural Giddiness)) && (EOD-)	Move to Tier 2, if (5d-BP > 135/85) && (after staying in this tier for 5 days)
Tier 2	Dual low dose combination (A+C)	Dual low dose combination	Move to Tier 1, if ((1d-BP < 135/85 for 7 consecutive days) II (1d-BP < 90/60 for 3 consecutive days) II (Symptoms of Hypotension like Postural Giddiness))	Move to Tier 3, if (5d-BP > 135/85) && (after staying in this tier for 5 days)

Tier 3	Dual full dose combination (A+C)	Dual full dose combination/ Triple combination/ Triple combination + spironolactone or Alpha blocker	Move to Tier 2, if ((1d-BP < 135/85 for 7 consecutive days) II (1d-BP < 90/60 for 3 consecutive days) II (Symptoms of Hypotension like Postural Giddiness))	Move to Tier 4, if (5d-BP > 135/85) && (after staying in this tier for 5 days)
Tier 4	Triple combination (A+C+B/ D/ Alpha blocker)	Triple combination/ Triple combination + spironolactone or Alpha blocker	Move to Tier 3, if ((1d-BP < 135/85 for 7 consecutive days) II (1d-BP < 90/60 for 3 consecutive days) II (Symptoms of Hypotension like Postural Giddiness))	Consider manual change of medication or withdraw

A= ACE inhibitor or ARB

C = Calcium channel blocker

B = Beta blocker

D = Diuretics

Note:

- EOD (End organ damage) + =
1. LVH present
 2. Albuminuria
 3. Evidence of Heart failure
 - A. Low ejection fraction
 - B. High pro-BNP
 - C. Clinical features
 4. Hypertensive retinopathy

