9.2 Secondary outcome

Blood pressure and antihypertensive medication related

1. **Change in blood pressure (Clinical and ambulatory blood pressure)** from baseline to 6 months and 2 year. Ambulatory and clinic blood pressure monitoring will be done as mentioned in the primary endpoint.
2. **Adequate control of blood pressure** as measured by ambulatory blood pressure monitoring at 1 year and 2 years

Criteria for adequate control of blood pressure is

- In <65 years < 130/80 mm Hg
- In 65 and above < 140/90 mm Hg

3. Number of antihypertensive medications at 6 months, 1 year and 2 years

Among those with adequate control, the number of antihypertensive medications will be calculated at baseline (after run in period) and subsequently every 3 months. Combination pills containing more than one group (of antihypertensive medications) will be considered based on the number of groups. Example: Lotrel which is a combination of Amlodipine and benazepril will be considered as 2 drugs. Further each drug will be categorized as high dose or low dose.

Table-5 for doses of commonly used antihypertensive medications

Drug name	Dose 1	Dose 2	Dose 3	Dose 4
Losartan	25 mg	50 mg		
Telmisartan	20 mg	40 mg	80 mg	
Olmesartan	5 mg	20 mg	40 mg	
Candesartan	16 mg	32 mg		
Captopril	12.5 mg	25 mg	50 mg	100 mg
Enalapril	5 mg	10 mg	20 mg	40 mg
Lisinopril	5 mg	10 mg	20 mg	40 mg
Ramipril	1.25 mg	2.5 mg	5 mg	
Hydrochlorothiazide	12.5 mg	25 mg	50 mg	100 mg

Chlorthalidone	25 mg	50 mg	100 mg	
Indapamide	1.25 mg	2.5 mg	5 mg	
Frusemide	20 mg	40 mg		
Prazosin	1 mg	2.5 mg	5 mg	
Terazosin	1 mg	2 mg	5 mg	
Doxazosin	1 mg	2 mg	4 mg	
Propranolol	10 mg	20 mg	40 mg	
Metoprolol	25 mg	50 mg	100 mg	
Atenolol	50 mg	100 mg		
Bisoprolol	5 mg	10 mg		
Amlodipine	5 mg	10 mg		
Cilnidipine	5 mg	10 mg	20 mg	
Nicardipine	20 mg	40 mg	80 mg	
Nifedipine	30 mg	60 mg	90 mg	
Felodipine	2.5 mg	5 mg	10 mg	

4. Frequency of introduction of new antihypertensive medications or dose increment of existing antihypertensive medications will be noted across both the groups and compared.

Metabolic parameters and biomarkers based

5. Change in metabolic parameters

- Will include anthropometric assessment (Height, Weight, BMI, waist circumference, Waist hip ratio, visceral fat), lipid profile including lipoprotein (a), apolipoprotein - A1, apolipoprotein - B, insulin resistance (measured by HOMA- IR) every 3 months till end of study

6. Change in cardiac and renal biomarkers

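### The de-escalation comparison keeps patients who take no drug at baseline and so cannot reduce

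*Protocol*

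**What the plan says.** Section 4.2, objective 3, sets both the comparison and its population. Within the patients who have adequate control, the aim is "to compare the de-escalation of dose or reduction in the number of antihypertensive medications from baseline", at 6 months, 1 year and 2 years. Section 9.2, outcome 3, repeats the population and says when drugs are counted: "Among those with adequate control, the number of antihypertensive medications will be calculated at baseline (after run in period) and subsequently every 3 months". Neither asks for at least one drug at baseline.

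Untreated patients are enrolled by design. Inclusion criterion 1 in Section 6 admits "both treatment naive & on treatment (includes monotherapy or multiple drugs", and the study population in the design synopsis reads "Monotherapy or more than one drug as well not on medications". Section 5 describes the run-in as being on existing therapy, so an untreated patient can reach baseline on no drug. Table 4 (Section 7.3.2, intervention arm) expects this: the entry condition for Tier 0 is "Initial no medicine & BP < 160/100 mm Hg", its reduction cell is empty, and it has only a rule for moving up.

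Objective 4 and outcome 4 separately compare new drug starts and dose increases between the groups, with no restriction to controlled patients.

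**The concern.** A reduction from baseline needs a baseline above zero. An untreated patient who stays at target without drugs has the best available course, yet can only be recorded as not having reduced. One who starts a drug during the trial and later stops it is back at zero, again with no reduction from baseline. The stated analysis set therefore contains patients for whom the event cannot occur in either arm, whatever the treatment does.

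At stake are the size and precision of the between-arm difference on the trial's main medication endpoint. An absolute difference would depend on how many untreated patients happen to be recruited and controlled, a share that the protocol does not fix. Section 7.2 mentions no stratification by baseline treatment, so the share may also differ between arms.

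**Working it through.** **The plan's own figure.** The protocol gives no sample size or power for this endpoint. Its only calculation is for the primary SBP comparison (Section 12.1: difference 5, SD 13, power 80%, alpha 5%, ratio 1:2). The normal approximation gives 1.5 × (1.96 + 0.84)² × 13²/5², about 80 in standard care and 160 in the intervention arm; the exact t test gives 81 and 162. The stated 83 and 166 are close, with power 0.81 by the t test. Dropout: 83/0.8 gives 104 and 166/0.8 gives 208. These figures hold up but do not bear on de-escalation; 83/166 serves below only as an upper bound on the patients analysed.

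**Reduction event.** Let q be the share of analysed patients on no drug at baseline, and p0 and p1 the event rates among treated patients in the standard and intervention arms. Untreated patients contribute no events, so the observed rates are (1−q)p0 and (1−q)p1.
- Risk difference: (1−q)(p1 − p0), if q is equal in both arms.
- Risk ratio: p1/p0, unchanged.

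**Power.** Two-sided 5% test of two proportions, pooled variance under the null and unpooled under the alternative. Assumed: p0 = 20%, p1 = 40%. The unrestricted analysis uses the diluted rates in all patients; the restricted one uses 20% v 40% in (1−q) of them, with a difference of 20 points throughout.

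| q | Difference, unrestricted | Power, 83/166: unrestricted v restricted | Power, 60% controlled: unrestricted v restricted |
|---|---|---|---|
| 10% | 18 points | 0.854 v 0.870 | 0.630 v 0.652 |
| 20% | 16 points | 0.789 v 0.827 | 0.555 v 0.598 |
| 30% | 14 points | 0.710 v 0.771 | 0.477 v 0.537 |
| 40% | 12 points | 0.618 v 0.702 | 0.399 v 0.471 |
| 50% | 10 points | 0.516 v 0.617 | 0.323 v 0.400 |

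Worked line for q = 30%, 83/166, unrestricted: rates 0.14 and 0.28, pooled 0.233. The null SE is 0.0569 and the alternative SE 0.0516. Then (0.14 − 1.96 × 0.0569)/0.0516 is about 0.55, which gives power 0.71.

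With 30% v 50% among treated patients, q = 30% and 83/166, the figures are 0.627 v 0.719.

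**Unequal shares.** Adequate control is observed after randomisation, so q among controlled patients may differ by arm. With 20% untreated in standard care and 30% in the intervention arm, the difference is 0.40 × 0.70 − 0.20 × 0.80 = 0.12. With the shares reversed it is 0.40 × 0.80 − 0.20 × 0.70 = 0.18. The factor (1−q) is then no longer exact.

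**Net change in drug count.** Untreated patients can still move up. Assume a treated-patient difference of −0.6 drugs and q = 30%. If untreated patients change equally in both arms, the overall difference is 0.7 × (−0.6) = −0.42. If they gain 1.5 drugs in standard care and 0.3 in the intervention arm, it is −0.42 + 0.3 × (0.3 − 1.5) = −0.78. The difference may shrink or grow.

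**The case against.** The strongest reply is that the protocol never commits to a responder analysis. Outcome 3 is headed as a number of drugs, and Section 12.2 compares quantitative variables by t test or Mann-Whitney. On a count, an untreated patient who stays at zero is distinguished from one who is started on two drugs. This stands: a reader might infer that dilution is certain, and the documents do not support that. It follows for the event wording of objective 3 on the difference scale, not for net count.

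Second, a reader might infer that untreated patients are scored nowhere. They are: objective 4 captures new drug starts for them, and objective 2 their blood pressure control. It does not follow that they belong in a reduction comparison.

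Third, the denominator of a secondary endpoint could be left to an SAP, which is not shown. Here, though, the protocol does name the set, and an SAP that follows it would keep these patients.

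Fourth, it is tempting to say that restriction by baseline treatment keeps the comparison randomised. That fails while adequate control, a post-randomisation condition, still decides who is analysed.

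Finally, Section 3 says "we will be studying reversal of hypertension through improvement of metabolic health", and a reader might infer that an endpoint of being drug-free and at target is required. It would be a reasonable addition, but its absence is not an error in objective 3.

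**Conclusion.** The point holds in a limited form. The stated set for objective 3 and outcome 3 includes patients who cannot have the event, and nothing in the protocol removes them. For a reduction event, the risk difference shrinks by the untreated share among analysed patients, and power is below that of the restricted analysis at every assumed share from 10% to 50%, although restriction uses fewer patients. At an assumed 30% the loss is about 6 points of power, whether all 83/166 or only 60% of them are analysed.

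These sizes rest on assumed event rates, an assumed untreated share and, for the (1−q) factor, equal shares in both arms; the protocol gives none of these. The risk ratio is not affected. The problem is confined to one secondary endpoint, and the primary comparison and its sample size are untouched. It is worth correcting because the correction is simple.

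**What to change.** In objective 3 and outcome 3:
- Limit the de-escalation or reduction comparison to patients taking at least one antihypertensive at the post-run-in baseline.
- State whether the measure is a reduction event or the net change in drug count.
- Make adequate control part of the outcome (reduced and controlled at the visit), not a condition for entering the analysis. Only then is the restricted comparison fully randomised.
- Report patients untreated at baseline under objective 4, with the proportion in each arm who remain drug-free.

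The cost is wording. Drug counts and ambulatory readings at the relevant visits are already planned (Sections 9.2 and 7.5.1). The downside is a smaller set for this one comparison: at an assumed 30% untreated, 83/166 becomes about 58/116. For a reduction event, the patients removed carry no information on de-escalation.
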